Project HEAL’s mentorship program is one of the first programs of its kind. Given the project’s nascence, its acceptability and effectiveness have not been evaluated, and Project HEAL has asked Drs. [name] and [name] and the Columbia Eating Disorders Research Unit (EDRU) to evaluate it by conducting a randomized controlled trial comparing mentorship to two other conditions also carried out by Project HEAL. The two comparison programs are a non-eating disorder-focused social support condition (for six months) and a wait-list control (for six months). In the social support condition, individuals with an eating disorder are matched with a “social support mentor” without a history of an eating disorder. Social support mentors coordinate social activities within Project HEAL and the community, such as participating in advocacy or leisure activities. Participants assigned to this condition engage in an activity per week (lasting approximately one hour) with their social support mentor and in some cases, 1-2 other mentees. Interactions are centered on the week’s activity (e.g., writing a letter to a representative, viewing museum exhibit), with an *intentional focus outside the eating disorder*. Wait-list participants engage in treatment with their outpatient providers for six months (as do patients in both active conditions), and then they are offered a mentor for six additional months. They may choose whether they prefer a peer mentor or a social support mentor. Interventions were developed by Project

HEAL and tailored to suit a research context with input from EDRU investigators. Program descriptions and manuals are provided for context.

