To evaluate feasibility, we will monitor mentee attendance and acceptability in both active conditions. To evaluate fidelity, mentors and mentees will be asked to complete a brief form (Appendix 1, “weekly report”) assessing meeting logistics (e.g., where the meeting occurred, number of contacts per week outside of meeting) and content of the meeting (e.g., topics discussed, activities). Peer mentors will be asked to complete an additional questionnaire assessing adherence to the peer-mentorship manual (Appendix 2, post-meeting mentor rating). Participants’ eating disorder symptoms, comorbid psychiatric symptoms, and health care costs and utilization will be assessed at pre- mid- and post-treatment to evaluate preliminary efficacy. Participants’ weight and BMI trajectories will also be evaluated by obtaining weight measures from the participant’s outpatient provider with participant permission. Outcomes for individuals who participate in the peer mentorship program will be compared with individuals who participate in the social support and wait-list conditions. **We will also evaluate characteristics of individuals participating as peer and social support mentors, including whether demographic characteristics and diagnostic history influence outcome of the mentorship.**

Specific Aims and Hypotheses

Concisely state the objectives of the study and the hypothesis or primary research question(s) being examined. There should be one hypothesis for every major study procedure or intervention. For pilot studies, it is important not to overstate the study's objectives. If there are no study hypotheses, describe broad study goals/aims.

Primary Aims and Hypotheses:

Aim 1. Evaluate the feasibility and acceptability of peer mentorship. Hyp 1a. Peer mentorship will demonstrate greater feasibility, as measured by higher attendance rates, compared to the active control intervention. Hyp 1b. Peer mentorship will demonstrate greater acceptability, as measured by higher acceptability ratings, compared to both control conditions.

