Assessments: All participants will complete monthly assessments of eating disorder symptoms, eating disorder quality of life, and co-morbid psychiatric symptoms throughout the six month randomized phase and then again at a 12-month follow up time point. Participants assigned to the wait-list condition will also complete monthly assessments throughout the "open label" phase in which they are receiving mentorship. On a monthly basis, patients' treatment providers will be contacted in order to obtain the patient's current height/weight from which to calculate BMI. Patient questionnaires will be administered using Qualtrics, a HIPAA-compliant applications accessible by smart phone or computer. If, during participation in an intervention or wait-list condition, a participant is hospitalized or returns to a higher level of care (e.g., residential treatment, partial hospitalization), he/she may resume participation in the mentorship component of the study only with permission from his/her treatment provider (a new letter must be obtained from primary provider). **All participants will complete a questionnaire assessing study acceptability of the study at the end of the 6 months period of mentorship or as soon as their participation in the study ends (e.g., if a participant discontinues after 3 months, they will be asked to complete the survey at that time).**

Mentor Procedures:

Individuals participating as mentors will be asked if they are willing to allow the study team to utilize data previously collected as part of interviewing and training to be a mentor. This data includes demographic information such as age and gender, as well as diagnostic history, for the peer mentors. Mentors will be informed about the study during a supervision call with the PI of the study and Project HEAL staff. Prior to reviewing the consent form during the telephone call with all mentors, all mentors will be sent a copy of the consent form to review ahead of time. Mentors will be asked to then speak individually with one of the study team members (the PI, a trained RA or other study clinician) to indicate whether or not they wish to participate in the study.

The information collected as part of the process of interviewing to be a mentor will be sent in a de-identified format. The code linking mentor information with the identifier will be transmitted by phone to the study team. Mentors will also be asked to fill out a brief 4-question survey using Qualtrics.

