Health Care cost: Estimated total health care costs related to the patient's eating disorder will be assessed using the Health Care Cost and Utilization Survey, developed by the research team. The survey asks participants to report the types and frequencies of a range of health services received including hospitalizations, residential treatment, outpatient visits (e.g., primary care, registered dietician) and tests (e.g., urine test, blood test), and mental health treatment (e.g., individual therapy, family therapy). Patients are also asked to report information pertaining to their insurance coverage and amount/percentages paid out-of-pocket for various services.

Acceptability of the study: Acceptability of the mentorship programs will be assessed using the Study Acceptability Form developed by the research team, modified from existing evaluation measures. The questionnaire asks participants to report on their experience with mentorship on dimensions of helpfulness, appropriateness, overall experience, matching expectations, recommend to friend, as well as specific questions pertaining to the alliance with mentor. Participants rate their answers on a 5- or 7-point scale or in open-ended dialogue boxes.

Research Related Delay to Treatment

Research involving participants who are in need of treatment invariably involves delay to care, and this delay is associated with risk. Scheduling of procedures must be carefully organized to minimize delay. Other delay must involve only that minimally necessary to accomplish the aims of the research while respecting subject well-being and safety. Describe the delay, by virtue of research participation in this study, before a participant can receive treatment of known efficacy or standard care routinely offered in the community.

All participants will be enrolled in treatment with a licensed provider concurrent with their participation in either peer mentorship, social support, or wait-list. The study involves three intervention arms, two of which are active (peer mentorship, social support) and one of which is a wait-list control. For individuals assigned to mentorship or social support, there may be a delay to intervention if a mentor or volunteer is unavailable to meet with the participant at the time that he/she enrolls in the study. For participants assigned to the wait-list, there will be a six-month delay before the participant receives an active intervention.

Clinical Treatment Alternatives

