Cover page

Official Title: Evaluation of the Communities of HEALing mentorship/support group program:
Assessment of preliminary efficacy

NCT number: NCT03317379

Document date: 3/23/2018

Statistical Analysis Plan

Intent-to-treat analyses will be used. Linear mixed models will be used to examine the relationship between group (peer, social support, wait list) and each outcome. Predictors in each model will be time, group, and their interaction. For all models, a random intercept will be included. The need for random slopes will be evaluated by examining model fit indices and testing the significance of the difference of the covariance estimate from zero. The peer group will be coded as the reference group to provide estimates and significance values for the difference between peer mentorship and each control condition.

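### The SAP's single linear mixed model for every outcome cannot be run as written for the once-only acceptability rating (Hyp 1b), suits several other outcomes poorly, and leaves open which coefficient or month is tested

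*SAP*

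**What the plan says.** The SAP is one paragraph. It specifies intention-to-treat analysis and states: "Linear mixed models will be used to examine the relationship between group (peer, social support, wait list) and each outcome". It continues: "Predictors in each model will be time, group, and their interaction". A random intercept goes into all models. On slopes it says: "The need for random slopes will be evaluated by examining model fit indices", together with a test of the covariance estimate against zero. Peer mentorship is the reference group "to provide estimates and significance values for the difference between peer mentorship and each control condition". No outcome is listed or exempted. The SAP does not say whether time is numeric or categorical, where time zero lies, or how month 12 enters.

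The protocol (Specific Aims and Hypotheses) places these under its primary aims:
- Hyp 1a: attendance, peer against social support only.
- Hyp 1b: "Peer mentorship will demonstrate greater acceptability, as measured by higher acceptability ratings, compared to both control conditions".
- Hyp 2a: larger reductions in EPSI scores.
- Hyp 2b and 2c: yes/no outcomes within diagnosis groups (BMI of at least 18.5; abstinence from bingeing or purging).
- Hyp 3: lower treatment cost, post-treatment and at one year.

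Acceptability is collected once per person (Study Procedures, Assessments): "at the end of the 6 months period of mentorship or as soon as their participation in the study ends". Assessment Instruments says the form asks participants to "report on their experience with mentorship on dimensions of helpfulness, appropriateness, overall experience". The Background section plans to monitor attendance and acceptability in the two active arms. It also says that wait-list participants have only their outpatient care for six months; "then they are offered a mentor for six additional months", peer or social support as they prefer.

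**The concern.** A model with time, time-by-group and a random intercept needs repeated measurements. Acceptability has one per person, so a primary-aim hypothesis has no analysis that can be run as stated. Its comparison with the wait list also lacks the object being rated.

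For the repeated outcomes the model can be fitted, but the difference between arms could be read as the group coefficient, the time-by-group slope or a difference at a named month. These answer different questions. If the choice is open when the data are seen, the deciding test can be picked afterwards.

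**Working it through.** The documents give no power, alpha or effect size, so there is no planned figure to reproduce. I take the random intercept to be at participant level; the SAP does not say.

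**1. Hyp 1b at nominal rating times.** With S and W marking social support and wait list, the fixed part is b0 + b1·S + b2·W + b3·t + b4·t·S + b5·t·W. If all rate at month 6, there are three distinct rows:
- Peer (1,0,0,6,0,0)
- Social support (1,1,0,6,6,0)
- Wait list (1,0,1,6,0,6)

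Three rows give rank 3 of 6. If the wait list rates after its later mentorship, about month 12 (an inference), its row is (1,0,1,12,0,12) and the rank is still 3. Social support minus peer is b1 + 6·b4, which is estimable. Wait list minus peer is b2 + 6·b3 + 12·b5, which mixes arm with time. With no wait-list ratings the rank is 2.

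With one rating per person, the variance is the sum of the intercept and residual variances. In a simulated set of 80 people the log-likelihood was −108.020977 for splits (0, 1), (0.1, 0.9), (0.5, 0.5), (0.9, 0.1) and (0.999, 0.001). The split is not identified. The group estimates did not change.

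**2. Hyp 1b with actual rating month as time.** People who stop early rate when they stop, so months vary and the rank becomes 6 of 6. Time then measures early exit, which happens after randomisation. Illustration: 20% stop early (1 − 80/100, implied by 80 completers from 100 enrolled), early ratings fall at months 1–5, and the true peer advantage is 0.50 SD. Estimated advantage at month 6:

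| Who stops early | Estimate |
|---|---|
| Lowest 20% on satisfaction overall (worst case) | 0.35 |
| Stopping–satisfaction correlation 0.5 | 0.46 |
| Correlation 0.3 | 0.49 |
| At random, or lowest 20% within each arm | 0.50 |

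**3. Hyp 1a.** Weekly reports over 26 weeks in two arms give rank 4 of 6. The two missing terms are the wait-list terms, which Hyp 1a does not need. One rate per person gives rank 2, a simple two-arm comparison. On the form of model, I assumed 27 per arm (80/3), 26 planned meetings, mean attendance 60% or 80%, and intraclass correlation 0.05–0.4. With no arm effect, plain binomial regression rejected in 18–57% of trials and quasi-binomial in 4.3–4.8%.

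**4. Hyp 2b.** Assumed: baseline BMI mean 19.0, SD 1.5, monthly steps SD 0.2–0.4, 13 or 27 per arm, no arm effect. The linear slope test with a random slope rejected in 1.7–5.0% of trials. Fitted arm means left the 0–1 range in 0–0.3% of trials. With BMI mean 20 and SD 1.2, they did so in 19% (13 per arm) and 4% (27 per arm). Firth-penalised regression of month-6 status rejected in 1.3–3.1% and 3.4–4.2%.

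**5. Repeated continuous outcomes.** In one simulated seven-visit data set, only the time origin was moved:

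| Time zero | Group coefficient, social support | Group coefficient, wait list |
|---|---|---|
| Baseline | 0.14 | −2.34 |
| Month 3 | 0.74 | −0.02 |
| Month 6 | 1.35 | 2.29 |

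The linear interaction stayed at 0.202 and 0.773. Numeric time gives 2 interaction terms; categorical time over months 0–6 gives 2 × 6 = 12.

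A slope and a month-6 contrast can also disagree. The least-squares slope over months 0–6 is Σ(t − 3)·y / 28. Illustration only, on no scale the protocol defines: peer falls from 50 to 20 at month 1 and stays there, giving (−3·50 + 3·20)/28 = −3.21. Control falls evenly from 50 to 30, giving −20/6 = −3.33. The slope slightly favours control, although peer is 10 points better at month 6.

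For an effect that builds evenly and then holds, six times the slope recovers 64% of it if complete by month 1, 86% by month 2, and 100–107% by months 3–6. Under a random-intercept model, relative signal-to-noise is slope × √28 against month-6 change/√2:
- Complete by month 1: (3/28) × √28 = 0.57, against 0.71.
- Taking two to six months: 0.76–0.95, against 0.71.

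**6. Hyp 3.** With numeric time, the arm difference in change is slope × months. The ratio of one year to month 6 is fixed at 12/6 = 2, so both stated time points share one test.

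**The case against.** The SAP may have been written with only the monthly measures in mind, and for those a linear mixed model is reasonable. Its wording sets no such limit, though, and on that reading Aim 1 has no analysis at all.

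Several stronger readings are tempting, and the documents do not support them:
- *Missing wait-list attendance undermines Hyp 1a.* It does not. Hyp 1a compares peer with social support only; the clash is with the SAP's three-level group term.
- *No contrast is named.* The SAP names peer against each control. What is missing is the coefficient or month. Hyp 2a speaks of reductions, so time-by-group is a natural reading, but it is not stated.
- *Acceptability cannot be analysed at all.* The peer versus social support difference is estimable once the surplus terms go. Even wait list versus peer can be computed without a time term if ratings exist. The objection there is comparability: such ratings follow later mentorship of a self-chosen type.
- *The linear model inflates type I error for yes/no outcomes.* With a random slope it did not in the check above.
- *Using rating month as time will dilute the effect.* The 0.35 is a worst case; other stopping patterns gave 0.46–0.50.

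It is also fair that slope against month 6 is partly a choice of estimand, and that the slope is often the more powerful test.

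**Conclusion.** The point holds and should be fixed. It is firm for Hyp 1b and moderate for the rest.

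For Hyp 1b, the time and interaction terms are aliased at nominal rating times (rank 3 of 6), and a participant-level intercept variance is never identifiable. Actual rating months repair the rank only by adjusting for early exit. Superiority over the wait list cannot be answered in the randomised phase, and Hyp 1b conflicts with the Background section's plan to monitor acceptability in the active arms. These conclusions rest on the documents and on one rating per person.

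For Hyp 2b and 2c, the gain from changing is interpretation and valid probabilities, not error control. For continuous scores, the gap is the unstated time coding and the unstated coefficient or month. For Hyp 3, the forced factor of 2 applies if time is numeric, which the mention of random slopes suggests but does not establish. The simulated sizes rest on the assumptions given with them.

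**What to change.** - **Hyp 1b:** linear or ordinal regression of the single rating, peer against social support, with no time term or random intercept. Report wait-list ratings descriptively and reword the hypothesis.
- **Hyp 1a:** drop the wait-list level. Model meetings attended out of planned meetings with a quasi-binomial or beta-binomial model, and state how weeks after discontinuation or suspension count.
- **Hyp 2b and 2c:** logistic regression of month-6 status adjusted for baseline status, within diagnosis group, Firth-penalised if cells are sparse. Report the risk difference beside it. A monthly GEE is not needed.
- **EPSI and other continuous repeated scores:** keep the linear mixed model, code time as categorical, and name the peer-versus-control difference in change from baseline to month 6 as the test.
- **Hyp 3:** name separate post-treatment and one-year contrasts. Note that the wait list is offered mentorship in months 6–12, so the one-year contrast is not against an unmentored group. Reconcile the one-year cost hypothesis with the Background section, which schedules cost assessment before, midway through and after treatment.

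The cost is SAP wording and modest programming. The month-6 contrast loses power to a slope when the effect takes two or more months to build (0.71 against 0.76–0.95) and gains when it appears in month 1 (0.71 against 0.57). Firth tests are conservative in small diagnosis groups. Hyp 1b gives up its wait-list claim. If the cost survey is not given at one year, that part of Hyp 3 needs an added survey or must be removed.

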Aim 2: Evaluate the impact of intervention condition on eating disorder symptoms. Hyp 2a. Participants in peer mentorship will have greater reductions in eating disorder symptoms, measured using the Eating Disorder Symptom Inventory (EPSI), compared to both control conditions. Hyp2b: For individuals who meet criteria for current or past anorexia nervosa, individuals assigned to peer mentorship will be more likely to achieve or maintain a BMI ≥ 18.5 , compared to both control conditions. Hyp2c: For individuals who meet criteria for current or past bulimia nervosa or binge eating disorder, individuals assigned to peer mentorship will be more likely to abstain from bingeing/purging and bingeing episodes, respectively, compared to individuals in either control condition.

Aim 3: Evaluate the impact of intervention condition on total cost for eating disorder treatment. Hyp 3. Estimated total cost for eating disorder treatment, measured using the Healthcare Utilization Survey, will be lower among peer mentorship participants compared to both control groups at (i) post-treatment and (ii) one-year follow up.

Exploratory Aim: Evaluate characteristics of individuals participating as peer and social support mentors. Exploratory hypothesis: Mentor characteristics and similarity between mentee and mentor characteristics will not influence mentee outcomes (acceptability, eating disorder symptoms, and estimated treatment cost).

Inclusion/Exclusion Criteria

This section details your study sample(s) and addresses the requirement for risk minimization. You may choose to divide your sample by population (healthy controls vs. subjects) or by procedure (subjects who will have an MRI) and then define different sets of criteria for each.

For each sample, create or insert a table to describe detailed criteria for study inclusion and exclusion and the method you will use to ascertain each criterion. The method of ascertainment may describe tests, scales and instruments. When relevant, indicate the level of training of the person who will make the assessment (e.g. clinical interview by a psychiatrist).

Inclusion/Exclusion Criteria needs to be numbered and listed in outline form (see Table template below)

Mentees (Adolescents or adults with anorexia nervosa, bulimia nervosa, or binge eating disorder):

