Additional pre-intervention procedures: Prior to study enrollment, participants will complete several questionnaires and provide documentation from their treatment team. Questionnaires will be administered using Qualtrics, a HIPAA-compliant application accessible by computer or smart phone, by which participants can access and complete online surveys. Assessment measures are described in detail below in the Assessment Instruments section. They will be used to assess baseline eating disorder symptoms, co-morbid psychiatric symptoms and health care cost and utilization. Participants will provide contact information for their primary provider and document his/her consent to contact his/her primary provider. Similar to consent forms, consent to speak with primary providers will be obtained verbally and signed hard copies will be collected. Primary outpatient treatment providers will be asked to complete a baseline medical evaluation form documenting that, in his/her opinion, the patient is enrolled in treatment *at a sufficient level of care given*. The form on which this information will be document is attached as an addendum (Appendix 3). Treatment providers will also be asked to provide documentation of the patient's medical stability. On a monthly basis, providers will be contacted by EDRU staff and asked to report the participant's height and weight and confirm medical stability and continued treatment engagement.

Interventions:

After a participant has signed consent and completed baseline screening measures, he or she will be randomized to a condition. Randomization schema will be developed and executed by EDRU research team. The participant will then be matched with an available mentor. Matching is based on geographic location and when possible, age, gender, and diagnostic subtype, (e.g., an individual with anorexia nervosa would not be matched with a mentor who has binge eating disorder)). Participants will enter the study on a rolling basis. After a participant is assigned to a condition, he or she will be contacted by Project HEAL staff and informed of treatment assignment. Participants assigned to mentorship or social support will be instructed that he/she will be contacted by his/her mentor/PH volunteer within five days.

Active intervention conditions

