Eating Disorder Symptoms: Eating disorder symptoms will be assessed monthly using the Eating Pathology Symptoms Inventory (1). The Eating Pathology Symptoms Inventory (EPSI) is a self-report questionnaire that includes 45 items covering 8 subscales: Body Dissatisfaction, Binge Eating, Cognitive Restraint, Purging, Restricting, Excessive Exercise, Negative Attitudes toward Obesity, and Muscle Building. Each item is scored on a five-point Likert-style scale (0 = Never; 4= Often) to describe how well each item describes the participant's experiences. Scores are derived by summing responses across the questions included in each subscale. The EPSI is part of the Phynx Toolkit, a NHGRI/NIDA-sponsored catalog of recommended standard measures of phenotypes (symptoms) for use in biomedical research. To assess frequency of bingeing and purging episodes, BN and BED patients will be asked to report the average number of episodes/week experienced within the past month on each monthly report of symptoms.

Eating Disorders Quality of Life: Quality of life as related to the patient's eating disorder will be measured using the Eating Disorder Quality of Life assessment survey (2). The EDQOL is a 30-item measure assessing the impact of the eating disorder on psychological, physical/cognitive, financial and work/school domains of life. Participants indicate the extent to which the eating disorder has resulted in a variety of consequences within the past 30 days (e.g., "How often has your eating disorder led to low grades?" on a 5-point scale ranging from 1 = "never" to 5 = "always." Higher scores indicate higher levels of QOL impairment. The measure has been validated and demonstrates good psychometric properties.

Comorbid psychiatric symptoms: Anxiety symptoms will be measured using the State Trait Anxiety Inventory (STAI) (3).The STAI is a well-validated 20-item measure used to assess trait-level anxiety. Each item is rated on a scale of 0 – 2, with total scores ranging from 0 – 40. Depressive symptoms will be measured using the Patient Health Questionnaire-9 (PHQ-9), a 9-item self-report questionnaire commonly used in clinical practice. The PHQ has demonstrated good psychometric properties and has high sensitivity and specificity (4).

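### For EPSI subscales, STAI and PHQ-9, a common baseline mean across arms would probably tighten the month-6 contrasts; the SAP model is valid as it stands, so this is an optional precision improvement

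*SAP*

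**What the plan says.** The SAP gives one model form for every outcome. Its fixed effects are: "Predictors in each model will be time, group, and their interaction". A random intercept is always included, and the rest is settled from the data: "The need for random slopes will be evaluated by examining model fit indices", together with a test of the covariance estimate. The peer arm is "coded as the reference group to provide estimates and significance values for the difference between peer mentorship and each control condition". The SAP does not say whether time is linear or categorical, which visits enter, or whether baseline is an outcome row. The random-slope clause points towards continuous time.

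In the protocol:
- Study Procedures (Additional pre-intervention procedures) says of the questionnaires: "They will be used to assess baseline eating disorder symptoms, co-morbid psychiatric symptoms and health care cost and utilization".
- Study Procedures (Interventions) then gives the order of events: "completed baseline screening measures, he or she will be randomized to a condition".
- Hypothesis 2a is about change: "Participants in peer mentorship will have greater reductions in eating disorder symptoms".
- Assessment Instruments defines the EPSI by subscale and gives no total: "Scores are derived by summing responses across the questions included in each subscale".
- The Background says of the wait-list arm, after its first six months: "then they are offered a mentor for six additional months".

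**The concern.** Because baseline is measured before allocation, any difference between arms in expected baseline score is zero by design. A model with time, group and their interaction, with baseline among the outcomes, still spends information estimating those differences. The same model with one common baseline mean uses the baseline score more efficiently.

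This matters because the trial is small. One hundred enrolled over three arms is about 33 per arm (100/3), and 80 completers is about 27 (80/3), if allocation is equal. Under the assumptions below, only fairly large month-6 differences are detectable, so precision from data already collected is worth having.

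The point applies to continuous outcomes with a stated pre-randomisation baseline: each EPSI subscale analysed, STAI and PHQ-9. It does not apply to attendance or acceptability (no baseline), to BMI ≥ 18.5 or abstinence (binary), to cost (different visit schedule), or to EDQOL (not named in the pre-intervention list).

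**Working it through.** **The plan's own figures.** The only sample-size numbers are 80 completers and 100 enrolled. 80/(1 − 0.20) = 100, so 20% loss is implied. No power, alpha, effect size, SD or correlation is given, so there is no power calculation to reproduce.

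**Assumptions.** Unit baseline variance; ICC 0.4-0.7; slope variance 0.005-0.02 per month squared; intercept-slope correlation −0.3 to +0.3; visits 0-6 (before wait-list participants are offered a mentor); even dropout to 80% at month 6; 33.3 per arm. The percentage cuts do not depend on the allocation ratio if dropout is equal across arms.

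**Contrast.** Peer minus one control, difference in change from baseline to month 6.

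**Method.** Generalised least squares, Var = (Σ X′V⁻¹X)⁻¹, with time coding the same in both models. Cut = 1 − Var(common baseline)/Var(free baselines).

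**Hand check.** Categorical time, random intercept, complete data, n per arm:
- Free baselines: (2/n) × 2(1 − ICC).
- Common baseline: (2/n) × (1 − ICC²).
- Ratio (1 + ICC)/2, so the cut is (1 − ICC)/2: 30% at ICC 0.4 and 15% at 0.7.

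**With the assumed dropout, random intercept only:**

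| ICC | Categorical | Linear |
|---|---|---|
| 0.4 | 26.0% | 26.9% |
| 0.5 | 21.6% | 20.7% |
| 0.6 | 17.2% | 15.4% |
| 0.7 | 12.9% | 10.8% |

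**With correctly specified random slopes:**

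| Correlation | Categorical | Linear |
|---|---|---|
| −0.3 | 17-29% | 17-32% |
| 0 | 6-23% | 4-22% |
| +0.3 | 0.5-17% | 0-14% |

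**In detectable difference** (80% power, two-sided 5%, no multiplicity adjustment, random intercept), from free to common baseline:
- Linear: 0.65 to 0.56 SD at ICC 0.4, and 0.46 to 0.44 at ICC 0.7.
- Categorical: 0.81 to 0.69 SD at ICC 0.4, and 0.57 to 0.54 at ICC 0.7.
- Arithmetic check: 0.65 × √(1 − 0.269) = 0.56.

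**Simulation with estimated variances** (REML, 33/33/34, dropout depending on the last observed value, 1,500 runs per ICC). Variance ratios, common to free, at ICC 0.4, 0.55 and 0.7 were 0.74, 0.82 and 0.84 (categorical) and 0.71, 0.83 and 0.86 (linear). Type I error was 4.6-5.7% (common) and 4.3-5.9% (free).

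**Other schedules.**
- Month 12 kept under one linear slope: 6-17% (random intercept) or 1-10% (uncorrelated slopes).
- The Background describes pre-, mid- and post-treatment assessment, which conflicts with the monthly schedule under Assessments. With months 0, 3 and 6 only, random intercept and complete data, the cut is about 15-33%.

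**Where the gain fails or has a price.**
- If random slopes exist but a random-intercept model is kept, variance can rise: about 1-4% at ICC 0.7, slope variance 0.02 and correlation +0.3, and more at +0.5.
- Under linear time with a random intercept, an effect that is zero to month 3 and then climbs to 0.50 SD at month 6 is estimated as 0.43-0.46 with a common baseline, against 0.49 with free baselines. Power barely moves: 55.3% to 57.7% at ICC 0.4, and 83.8% to 84.3% at ICC 0.7.
- An effect that reaches 0.50 SD by month 3 and stays flat is estimated as 0.54-0.57, against 0.51.
- If the trend is truly linear, the categorical common-baseline model has 14-34% higher variance than the linear free-baseline model (random intercept).

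**Design check.** With categorical time there are 7 × 3 = 21 mean parameters. Dropping only the group main effect leaves the rank at 21. Removing the two baseline arm terms gives 19. With linear time, dropping group takes the rank from 6 to 4.

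**The case against.** The strongest reply is that nothing is broken. Time, group and their interaction target Hypothesis 2a directly, and the analysis is valid under randomisation. Replacing it is an efficiency preference. That stands, and it sets the grade.

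A second reply is that the change has a price. Under linear time, the likelier reading of the SAP, a common intercept pulls a late effect down and pushes an early-plateau effect up. For the late effect the variance cut is almost cancelled. Under categorical time that sensitivity disappears, but the move from linear to categorical can itself cost precision. The gain also relies on an adequate covariance model, and the SAP retains slopes only if fit and significance support them. These points also stand.

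A third is that every percentage rests on covariances that the documents do not give, and on baseline being an outcome row, which the SAP does not say. True. The wording of Hypothesis 2a and the lack of a baseline covariate favour that reading without settling it. The ±0.3 limit also matters: at ±0.5 the upper end under linear time reaches 41-43%, while the lower end stays near zero.

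What survives is narrower. For plausible covariances the common-baseline model usually gives a tighter contrast from data already collected.

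**Conclusion.** The point holds as an optional precision improvement for EPSI subscales, STAI and PHQ-9. It does not identify a defect.

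Under the stated assumptions the variance cut is 11-27% with a random intercept only, and 0-32% with correctly specified slopes and correlations within ±0.3. For the random-intercept case that is worth about 12-37% more participants (1/0.89 = 1.12; 1/0.73 = 1.37). Keeping month 12 under linear time reduces the cut to 6-17% or 1-10%.

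A reader might infer three stronger things, none of which the documents support:
- *That the SAP analysis is biased or invalid without baseline adjustment.* It is not. Randomisation makes the arm baseline means equal in expectation, and the free-baseline contrast is unbiased.
- *That the gain is certain and without cost.* It can be nil when intercept and slope are positively correlated, can turn into a small loss if needed slopes are left out, and under linear time trades some robustness for precision.
- *That changing to categorical time is itself a gain.* If the trend is linear, that change costs precision.

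**What to change.** For the continuous outcomes with a pre-randomisation baseline, add two or three sentences to the SAP that state the time coding, say how the baseline value is used, and name the month-6 peer-versus-social-support and peer-versus-wait-list differences as the contrasts.

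- **Categorical time:** keep baseline in the outcome vector and fit one common baseline mean by removing the baseline arm terms explicitly; dropping the group main effect alone changes nothing. Alternatively, model post-baseline visits adjusted for the baseline value, with its coefficient free to vary by visit if random slopes are kept. In the simulation this matched the common-baseline model (0.74, 0.82, 0.84 of the free-baseline variance). Test the month-6 arm differences, not a time-by-group slope.
- **Linear time, coded 0 at baseline:** drop the group main effect and keep time and time-by-group. The contrast is 6 times the slope difference. Report the free-baseline model as a sensitivity analysis, because the common intercept is more sensitive to non-linear effects.

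The choice between linear and categorical time is a separate robustness decision and should not be presented as a precision gain. The change needs no new data, visits or participant burden. Its costs are the sensitivity to non-linear effects under linear time and the reliance on an adequate covariance model.
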